4.4.2 Secondary Efficacy Endpoints

4.4.2.1 MFM Total Score

The change from baseline in the MFM total score and the absolute value at each time-point will be summarized using descriptive statistics (following the missing data rules defined in Section 4.4.1.1). Mean changes in the MFM total score and corresponding 95% CIs over time will also be presented graphically. Summaries will be presented overall and by the treatment received in the previous Trophos study. The MFM total score is calculated as follows:

$$\text{MFM-32 total score (D1+D2+D3) (\%)} = \sum \text{all items scores} * 100 / 96 = (\sum \text{MFM-32 D1 items scores} + \sum \text{MFM-32 D2 items scores} + \sum \text{MFM-32 D3 items scores}) * 100 / 96$$

$$\text{MFM-20 total score (D1+D2+D3) (\%)} = \sum \text{all MFM-20 items scores} * 100 / 60 = (\sum \text{MFM-20 D1 items scores} + \sum \text{MFM-20 D2 items scores} + \sum \text{MFM-20 D3 items scores}) * 100 / 60$$

A comparison with natural history data will also be performed for the MFM total score, as described for the MFM D1+D2 score in Section 4.4.1.2.

4.4.2.2 PedsQL

The change from baseline in the total score and in each domain score, and the absolute values at each visit, will be summarized using descriptive statistics for the PedsQL 4.0 Generic Core scale (patients 5+ years) and the PedsQL 3.0 Neuromuscular module (patients 5-18 years only). Within each module, data will be pooled across age bands. Summaries will be presented separately for patient self-report and caregiver-report. For patient self-report, the data will also be summarized by age group: < 13 years and 13+ years for the core module, and < 13 years and 13-18 years for the neuromuscular module.

For scoring purposes, scale items are linearly transformed to a 0-100 scale (0 = 100, 1 = 75, 2 = 50, 3 = 25 and 4 = 0) so that higher scores indicate better health related quality of life. In accordance with the PedsQL manual, if more than 50% of the items in the scale are missing, the Scale Score will not be computed. If 50% or more items are completed, the mean of the completed items in a scale will be imputed. The mean score will be calculated as the sum of the item scores divided by the number of items answered.

4.4.2.3 WPAI:CG

The change from baseline in the WPAI:CG outcomes and the absolute value at each visit will be summarized using descriptive statistics. The WPAI:CG consists of four

questions about the effects of SMA on the following: employment status; hours missed due to patient caregiving; hours missed due to other reasons; hours actually worked; and two questions that measure the degree to which patient caregiving affected productivity (presenteeism) and regular daily activities. WPAI:CG outcomes are expressed as impairment percentages, with higher numbers indicating greater impairment and less productivity. The outcomes are calculated as follows:

Percent work time missed due to patient caregiving: $(Q2 / [Q2 + Q4]) * 100$

Percent impairment while working due to patient caregiving: $(Q5 / 10) * 100$

Percent overall work impairment due to patient caregiving: $(Q2 / (Q2 + Q4) + [(1 - (Q2 / (Q2 + Q4))) * (Q5 / 10)]) * 100$

Percent activity impairment due to patient caregiving: $(Q6 / 10) * 100$

where

Q1: currently employed

Q2: hours missed due to patient caregiving

Q3: hours missed due to other reasons

Q4: hours actually worked

Q5: degree patient caregiving affected productivity while working

Q6: degree patient caregiving affected regular activities

4.4.2.4 SMA Related Medical Complications and Procedures

SMA related medical complications and procedures will be collected through the adverse event (AE) reporting of the study and through the reporting of on-study SMA related surgeries and procedures. Events will be identified by applying a prospectively defined basket of MedDRA lowest level terms to the AE dataset and to the on-study SMA related surgery and procedure dataset.

For each event recorded, the term entered by the investigator describing the event (the 'verbatim term') will be assigned to a standardized term (the 'lowest level term') based on the most up-to-date version of MedDRA. Data displays of SMA related medical complications and procedures will be performed using the system organ class and lowest level terms. For summaries of event incidences, patients who experience the same event on more than one occasion will be counted once in the calculation of the event frequency at the highest intensity reported. Each table will also present the number and percentage of patients who experience at least one SMA related medical

complication or procedure during the study (including safety follow-up period) and the total number of events reported.

On-study SMA related surgeries and procedures which have not been identified by the MedDRA basket will be summarized separately.

Similar analyses will be performed for SMA related medical complications occurring in the NatHis-SMA comparison population. The pre-specified MedDRA basket will be applied to the AE dataset for this population, and the data will be summarized as described for the ITT population. AEs which have not been identified by the MedDRA basket and have been classified as 'due to the disease' by the investigator will also be summarized.

The AE rate adjusted for patient years (all occurrences, by lowest level term) and corresponding exact 95% CIs for the event rate in the ITT and NatHis-SMA comparison populations will also be presented. The event rate per 100 patient-years is computed as follows:

$$\text{AE rate} = (\text{number of AEs observed} / \text{total patient-years at risk}) * 100$$

where for study BN29854

Total patient-years at risk = sum across all patients of the time intervals (in years) between start of study therapy up to 28 days after study withdrawal/completion

and for the NatHis-SMA study

Total patient-years at risk = sum across all patients of the time intervals (in years) between study start and study withdrawal/completion

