## **2.2 SECONDARY OBJECTIVES**

The secondary objectives for this study are as follows:

- To evaluate effectiveness of olesoxime compared to the natural history of disease in patients with SMA, as measured by MFM D1+D2 and MFM Total scores.
- To evaluate the disease associated medical complications and procedures in olesoxime treated patients compared to the natural history of disease, focusing on their nature, frequency of occurrence, and severity.
- To evaluate the disease course between last visit of the studies TRO19622CLEQ1275-1 and TRO19622CLEQ1115-1, and baseline assessment in this study, as measured by motor functional scales (e.g., MFM) and as measured by nature, frequency, and severity of medical procedures.

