4.1.5 NatHis-SMA Comparison Population

The NatHis-SMA comparison population will include all patients enrolled in the NatHis-SMA study aged between the minimum age in the ITT population minus 2 years up to the maximum age in the ITT population plus 5 years, with Type 2 or non-ambulatory Type 3 SMA. This population will be used to evaluate the incidence of SMA related medical complications in olesoxime-treated patients compared to the natural history of the disease.

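### The complications tables draw on AE plus procedure records in BN29854 but on AE records only in NatHis-SMA, so the incidence counts are not like for like

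*SAP*

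**What the plan says.** Protocol 2.2 makes this a secondary objective: "To evaluate the disease associated medical complications and procedures in olesoxime treated patients compared to the natural history of disease". Protocol 3.3.2.1 names the proportion of patients with such complications and procedures as a secondary efficacy measure.

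SAP 4.4.2.4 identifies BN29854 events by "applying a prospectively defined basket of MedDRA lowest level terms to the AE dataset and to the on-study SMA related surgery and procedure dataset". Each BN29854 table gives the number and percentage of patients with at least one SMA related medical "complication or procedure during the study (including safety follow-up period) and the total number of events reported". Procedures outside the basket are kept apart: "On-study SMA related surgeries and procedures which have not been identified by the MedDRA basket will be summarized separately".

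For the comparator the wording narrows: "Similar analyses will be performed for SMA related medical complications occurring in the NatHis-SMA comparison population", and "The pre-specified MedDRA basket will be applied to the AE dataset for this population". The comparator data are then to be summarized in the way set out for the ITT population. SAP 4.1.5 gives the comparison population the same narrower purpose; it is "used to evaluate the incidence of SMA related medical complications in olesoxime-treated patients".

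SAP 4.4.2.4 also plans a rate per 100 patient-years with exact 95% CIs in both populations. It is called an AE rate and its numerator is the number of AEs observed.

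**The concern.** One basket is run over two datasets in the trial and over one in the comparator, and the results are laid out in the same format. A reader who puts the two tables side by side is comparing complications plus procedures with whatever reached the comparator's AE data.

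The second BN29854 dataset is not redundant. Under Protocol 5.3.5.9, a hospitalization for a preexisting condition is not reported as an AE when elective surgery became necessary during the study through expected disease progression and the patient has had no AE. Surgery of that kind can sit in the procedure dataset alone.

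At stake is a descriptive reading of a secondary objective. Extra events on the olesoxime side could mask a real reduction in complications. Separately, the procedures half of the objective has no stated comparator at all.

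**Working it through.** The SAP gives no event count, power or target difference for this comparison, so there is no figure to reproduce. The check is first textual, then illustrative.

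**Sources side by side (SAP 4.4.2.4)**

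| Quantity | BN29854 | NatHis-SMA | Same source? |
|---|---|---|---|
| Patients with at least one event | AE + procedure data | AE data | No |
| Total events | AE + procedure data | AE data | No |
| Rate per 100 patient-years, numerator | AEs, as worded | AEs, as worded | Yes, as worded |

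**Event counts.** Let f be the number of events found only in the BN29854 procedure dataset, divided by AE-sourced basket events. The documents do not give f; I take 0 to 0.5. With equal true AE rates and equal follow-up, the pooled BN29854 count relative to the AE-only comparator is 1 + f: 1.05, 1.10, 1.20, 1.30 and 1.50 at f = 0.05, 0.10, 0.20, 0.30 and 0.50. Counted from AEs on both sides it is 1.00 for any f. A procedure also recorded as an AE adds nothing to f unless it is counted twice, and the SAP gives no rule on that.

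**Percentage of patients.** Each patient counts once, so the percentage moves less. Assume Poisson events at the same rate λ per year in every patient and T = 2 years; the percentage is 1 − exp(−λ(1 + f)T).

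| λ | f = 0 | f = 0.10 | f = 0.30 |
|---|---|---|---|
| 0.2 | 33.0% | 35.6% | 40.5% |
| 0.5 | 63.2% | 66.7% | 72.7% |
| 1.0 | 86.5% | 88.9% | 92.6% |

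At f = 0.30 the ratios are 40.5/33.0 = 1.23, 72.7/63.2 = 1.15 and 92.6/86.5 = 1.07, against 1.30 for events.

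**If NatHis-SMA recorded procedures as AEs.** Let g be the fraction of its other basket AEs made up of events that BN29854 would hold only as procedures. The pooled comparison becomes (1 + f)/(1 + g), which is 1.00 when f = g. An AE-only BN29854 count against that comparator would be 1/(1 + g): 1/1.10 = 0.91 at g = 0.10 and 1/1.30 = 0.77 at g = 0.30, now in olesoxime's favour.

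**Follow-up length.** NatHis-SMA patients are followed for 12 to 24 months (SAP 4.1.3.2); BN29854 may run up to 4 years after the last enrollment (Protocol 3.2). With AE-only counting and λ = 0.5 in both studies, 1 − exp(−λT) is 39.3% at 1 year, 63.2% at 2 years and 86.5% at 4 years. Crude percentages therefore differ through follow-up alone.

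**Rate denominator.** BN29854 patient-time runs to 28 days after withdrawal or completion; NatHis-SMA time stops at withdrawal or completion. If those 28 days yield no events (worst case), the BN29854 rate is multiplied by T/(T + 28/365.25): 0.929, 0.963 and 0.981 at T = 1, 2 and 4 years. Were procedure records to enter the numerator, the two effects would cancel at f = (28/365.25)/T = 7.7%, 3.8% and 1.9%.

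**The case against.** The strongest reply is that the SAP already contains a comparison with the same stated source on both sides. The patient-year rate is the quantity given with confidence intervals in both populations for these events, and it is worded as AEs only. The SAP also frames the NatHis-SMA comparison as one of complications, shows results by lowest level term so that procedure terms can be seen on their own lines, and does no formal testing (SAP 4.4).

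Most of this stands. Nothing shows the rate to be inflated; its numerator needs confirming, because the same paragraph also calls it an event rate and the section's events come from both datasets. The term-level display does not rescue the at-least-one and total-event lines, which pool terms. A descriptive comparison still needs matching sources.

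A reader might infer that the whole natural history comparison is biased against olesoxime. The documents do not support that. They do not describe how NatHis-SMA recorded procedures, and the extra 28 days of BN29854 patient-time can pull the rate the other way. A reader might also take a higher count on the olesoxime side to mean an exaggerated benefit; more complications counted under olesoxime would make it look worse.

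**Conclusion.** The mismatch is in the text and affects the incidence tables: patients with at least one event, and total events. Events found only in the BN29854 procedure dataset add to the olesoxime count. The size is unknown; the 1.05 to 1.50 range for event counts rests entirely on assumed values of f, equal true AE rates and equal follow-up, and percentages of patients would move less. The net direction is not established, because it depends on NatHis-SMA's AE conventions. The patient-year rate stands as worded. The point bears on a descriptive secondary objective and leaves the primary safety analysis untouched. It should be corrected because the plan's own counting rule creates the mismatch and removing it is cheap.

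**What to change.** In SAP 4.4.2.4:

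1. For tables set beside NatHis-SMA, add a BN29854 version counted from the AE dataset only, with procedure terms shown separately from complication terms. Keep the pooled AE-plus-procedure table as a BN29854-only summary.
2. Confirm that the numerator of the patient-year rate excludes procedure-dataset records.
3. Count an event recorded in both BN29854 datasets once.
4. State how NatHis-SMA captured procedures. If it has procedure data, apply the basket to them; otherwise state that the procedures part of the secondary objective has no natural history comparator.
5. Base the between-study comparison on the patient-year rate, not on crude percentages, because follow-up lengths differ. AE-only counting does not cure that difference.

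The cost is a few sentences and one extra table; the BN29854 steps need no new data. The downside is that AE-only counting could undercount BN29854 surgery if NatHis-SMA recorded such surgery as AEs, which is why procedure terms should be on separate lines.

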4. STATISTICAL METHODS

4.1 ANALYSIS POPULATIONS

4.1.1 Intent-to-Treat Population

The intent-to-treat (ITT) population will include all patients who received at least one dose of study medication and have at least one post-baseline assessment of MFM. The ITT population will be the primary population for efficacy analyses.

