4.1.2 Safety Population

The safety population will include all patients who received at least one dose of study medication. All safety analyses will be based on the safety population.

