4.1.3.2 NatHis-SMA

NatHis-SMA is a prospective natural history study sponsored by Roche and the Institute of Myology (Roche no. BP29540, ClinicalTrials.gov identifier: NCT02391831) that aims to characterize the disease course in SMA Type 2 and Type 3 patients using standardized evaluations, including the MFM. The study includes patients between 2 and 30 years of age from 9 centers in France, Belgium and Germany. Patients will remain in the study for a period of 12 to 24 months between 2015 and 2018.

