4.4 EFFICACY ANALYSIS

As this is a single arm, open-label study no formal hypothesis testing will be performed. Data collected during the treatment phase of this study will be summarized using descriptive statistics and will be compared with observational data describing the natural history of the disease.

The baseline value will be defined as the last non-missing value recorded prior to or on the first day of the study drug (Study Day 1).

Post-baseline efficacy assessments (scheduled every 26 weeks), including assessments performed at an early discontinuation visit, will be assigned to a scheduled study visit based on the following time windows:

Visit	Study Day	Time Window (in Study Days)
V3 (Week 26)	183	Day 2 – Day 274
V5 (Week 52)	365	Day 275 – Day 456
V6 (Week 78)	547	Day 457 – Day 638
V7 (Week 104)	729	Day 639 – Day 820
V8 (Week 130)	911	Day 821 – Day 1002
V9 (Week 156)	1093	Day 1003 – Day 1184
V10 (Week 182)	1275	Day 1185 – Day 1366
V11 (Week 208)	1457	Day 1367 – Day 1548
...		

If multiple valid values for a variable are recorded in the same time window, the record closest to the scheduled study visit will be selected for summary of the data.

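### SAP 4.4.2.4 puts exact intervals on recurrent-event rates, so they are too narrow for frequently recurring terms, and it takes the olesoxime rate from the MFM-conditional ITT set instead of the safety population

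*SAP*

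**What the plan says.** SAP 4.4.2.4 introduces the rate as "The AE rate adjusted for patient years (all occurrences, by lowest level term", divides it by total patient-years at risk, and adds that "corresponding exact 95% CIs for the event rate in the ITT and NatHis-SMA comparison populations will also be presented". The distribution behind the exact interval is not named. No robust variance, overdispersed model or resampling by patient is mentioned. Protocol 5.3.5.3 has each recurrence entered as a separate adverse event, so one patient can add several events to a term.

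The same SAP section also gives incidences in which "patients who experience the same event on more than one occasion will be counted once in the calculation of the event frequency". No interval is stated for these.

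On populations, the SAP defines ITT (4.1.1) as "all patients who received at least one dose of study medication and have at least one post-baseline assessment of MFM". For safety (4.1.2), "The safety population will include all patients who received at least one dose of study medication". On the other side of the comparison (4.1.5), "The NatHis-SMA comparison population will include all patients enrolled in the NatHis-SMA study" within an age band and with Type 2 or non-ambulatory Type 3 SMA; no MFM condition applies.

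**The concern.** Comparing the frequency of complications with natural history is a secondary objective (Protocol 2.2). SAP 4.4.2.4 plans no test and no rate ratio, so a reader will set the two intervals side by side. They are the only measure of uncertainty stated there for that comparison.

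Independence is doubtful on the protocol's own account. Section 1.1 describes pulmonary infections as frequent, and section 3.3.4 describes the disease as heterogeneous. If some patients are prone to repeat events, the total count varies more than a Poisson count, and the interval overstates precision in both studies.

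The ITT condition adds an asymmetry. A patient who dies or leaves with no post-baseline MFM is removed from the olesoxime rate together with his or her complications. The same adverse events still appear in the safety summaries of SAP 4.6.

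**Working it through.** The plan gives no event rate, count or sample size for this analysis, so there is no figure of its own to reproduce. The check asks how the planned interval behaves over a range of stated assumptions.

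**Inputs from the documents**
- All occurrences, by lowest level term, exact 95% interval (SAP 4.4.2.4).
- BN29854 size: at most 171 patients (Protocol 3.1.1); 119 with analysed baseline samples (Protocol 1.2.2).
- NatHis-SMA follow-up: "Patients will remain in the study for a period of 12 to 24 months between 2015 and 2018" (SAP 4.1.3.2).

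**Assumptions**
- 130 olesoxime patients × 3 years = 390 patient-years.
- 60 NatHis-SMA patients × 1.5 years (midpoint of 12 to 24 months) = 90 patient-years.
- Exact means exact Poisson: limits χ²(0.025; 2x)/2 and χ²(0.975; 2x+2)/2, divided by patient-years, for x events.
- Patient rates are gamma distributed with variance k relative to a mean of 1.

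**Step 1: variance.** With μ expected events per patient, variance/mean of the total count = 1 + kμ. The standard error is therefore √(1 + kμ) times the Poisson value. This ratio does not depend on the number of patients and grows with follow-up.

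**Step 2: coverage on the olesoxime side** (20,000 gamma-Poisson simulations per cell)

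| Rate per 100 patient-years | Expected events | μ | 1 + kμ, k = 1 / 2 | Coverage, k = 1 / 2 |
|---|---|---|---|---|
| 5 | 19.5 | 0.15 | 1.15 / 1.30 | 95.6% / 94.5% |
| 10 | 39 | 0.30 | 1.30 / 1.60 | 93.3% / 90.3% |
| 20 | 78 | 0.60 | 1.60 / 2.20 | 89.5% / 83.3% |
| 50 | 195 | 1.50 | 2.50 / 4.00 | 79.5% / 67.9% |

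With independent events (k = 0) coverage is 95.4% to 96.8%. A hand check at 50 per 100 patient-years with k = 2: the interval spans 1.96/√4 = 0.98 true standard errors each side, and 2Φ(0.98) − 1 = 67%. With 119 to 171 patients, coverage is 89% / 82–83% at 20 and 79% / 67–68% at 50.

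With milder clustering (k = 0.25 / 0.5), coverage is 96% / 95% at 10, 94% / 93% at 20 and 91% / 87% at 50.

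**Step 3: NatHis-SMA side.** Follow-up is shorter, so μ is smaller: coverage is 93.9% / 91.2% at 20 and 88.6% / 81.7% at 50 (k = 1 / 2).

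**Step 4: one interval in full.** Take 119 × 3 = 357 patient-years and 107 events, or 30 per 100 patient-years. The planned interval is 24.6 to 36.2. With μ = 0.9, allowing for clustering as 30 × exp(±1.96√((1 + 0.9k)/107)) gives 23.1 to 38.9 for k = 1 and 21.8 to 41.2 for k = 2.

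**Step 5: two intervals side by side.** With equal true rates, the two exact intervals fail to overlap in 1.8% / 3.6% of trials at 20 and 5.1% / 10.6% at 50 (k = 1 / 2). The figure is 0.7% under independence and 0.7% to 1.0% with robust intervals.

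**Step 6: robust interval, olesoxime side.** Coverage is 94.9% / 94.6% at 20 and 94.8% / 94.0% at 50. Widths per 100 patient-years are 11.4 / 13.4 against 9.1 exact at 20 (25% / 47% wider) and 22.4 / 28.4 against 14.3 at 50 (57% / 99% wider). It fails for very rare terms: 79% coverage at 2 per 100 patient-years in 60 × 1.5 years, where the exact interval covers 99%.

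**Step 7: ITT against safety.** Background rate 0.2 per year; L of 130 patients lost, each with t years at f times that rate. Safety rate = [(130 − L) × 3 × 0.2 + L × t × f × 0.2] / [(130 − L) × 3 + L × t].
- L = 2, t = 0.3, f = 3: (76.8 + 0.36)/(384 + 0.6) = 0.2006, +0.3%.
- L = 4, t = 0.3, f = 5: (75.6 + 1.2)/(378 + 1.2) = 0.2025, +1.3%.
- L = 4, t = 0.5, f = 10: (75.6 + 4)/(378 + 2) = 0.2095, +4.7%.

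**The case against.** The strongest reply is about weight. The section also reports incidence once per patient, with totals of events beside numbers of patients, so clustering will be visible. No hypothesis is tested (SAP 4.4) and no overlap rule exists, so the non-overlap figures describe an informal reading and not a planned decision. Lowest level terms are fine-grained. A term needs 78 occurrences in 390 patient-years to reach 20 per 100, and nothing shows that any single term will. Milder clustering gives smaller losses. All of this stands. It limits how many terms are affected, but it does not make the interval correct for those that recur often.

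On the population, ITT follows from the documents' own labels: Protocol 3.3.2.1 and SAP 2.1.2 treat complications as a secondary efficacy measure. SAP 4.4 counts "Post-baseline efficacy assessments (scheduled every 26 weeks), including assessments performed at an early discontinuation visit", so many early stoppers stay in ITT. That also stands, and it is why the effect is small.

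Against the remedy, a switch at 10 occurrences per population can put different methods on the two sides of one term: in 59% of simulated trials at 10 per 100 patient-years. This shows no harm. Non-overlap under equal rates stayed at or below about 1% even with mixed methods. Requiring both populations to reach 10 covered slightly worse (92% against 94% at 10 per 100 patient-years, k = 2).

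**Conclusion.** Both parts hold. The planned interval is adequate for terms at about 5 per 100 patient-years or fewer and too narrow for frequent ones: about 89% / 83% coverage at 20 and 79% / 68% at 50 on the olesoxime side, for k = 1 / 2. The size rests on k, the event rates, the NatHis-SMA sample size, mean follow-up and the Poisson reading of exact, none of which the documents give. More patients would not cure it.

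The ITT asymmetry is real but modest, and it can only lower the olesoxime rate if the dropped patients have more events than the rest. No net direction of bias is claimed for the comparison as a whole. The plan should be changed, because the cost is low and the comparison serves a secondary objective. Nothing here threatens a formal test, since none is planned.

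**What to change.** In SAP 4.4.2.4:

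- Compute the BN29854 rate on the safety population of SAP 4.1.2. Align the sentence there that describes the NatHis-SMA summary by reference to ITT, and state whether the age limits in 4.1.5 stay tied to ITT.
- Name the exact interval as Poisson and keep it for a term with fewer than 10 occurrences in a population. At 10 or more, use a patient-level robust-variance interval with a log person-time offset; a negative-binomial model or a bootstrap by patient would also serve. In simulation this rule covered 93% to 99% for rates of 1 to 50 per 100 patient-years, both study sizes and k = 0 to 2.
- Optionally, for the overall basket only, add a supportive rate ratio adjusted for age, sex, SMA type and baseline MFM D1+D2.

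The cost is two main SAP sentences with small conforming edits, and modest programming; no new data are needed. The price is wider intervals for frequent terms and two interval methods in one table, sometimes within one term, so the method should be marked beside each interval.

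### The SMA complication comparison requires a post-baseline MFM of olesoxime patients but not of NatHis-SMA patients, so some treated patients' events and follow-up are left out on one side only

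*SAP*

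**What the plan says.** Protocol 2.2 sets as a secondary objective: "To evaluate the disease associated medical complications and procedures in olesoxime treated patients compared to the natural history of disease". SAP 4.1.5 creates a dedicated comparator to "evaluate the incidence of SMA related medical complications in olesoxime-treated patients compared to the natural history of the disease".

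SAP 4.4.2.4 names the BN29854 population twice. For incidence, the NatHis-SMA events are handled in parallel: "the data will be summarized as described for the ITT population". For rates per 100 patient-years, exact intervals are planned for the "event rate in the ITT and NatHis-SMA comparison populations will also be presented".

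The two populations are defined differently:

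- ITT (SAP 4.1.1; Protocol 6.1 agrees): "all patients who received at least one dose of study medication and have at least one post-baseline assessment of MFM".
- NatHis-SMA comparison population (SAP 4.1.5): it "will include all patients enrolled in the NatHis-SMA study aged between the minimum age in the ITT population minus 2 years" and the ITT maximum plus 5 years, with Type 2 or non-ambulatory Type 3 SMA. No follow-up assessment is required.

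For BN29854, SAP 4.4.2.4 starts time at risk at first dose. SAP 4.1.2 already defines a safety population of all dosed patients, with no MFM condition.

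**The concern.** Requiring a post-baseline MFM makes sense when the outcome is change in MFM. Complication rates are built from the adverse event and procedure records, which exist whether or not an MFM was done. Here the condition only selects patients, and it does so on one side.

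It also looks into the future. Time at risk runs from first dose, but membership depends on an assessment first scheduled at Week 26. An ITT patient cannot, by construction, have died between first dose and first post-baseline MFM. A NatHis-SMA patient can.

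This bears on one of the three secondary objectives, and Protocol 3.3.2.1 expects an effective treatment to lower the incidence of comorbidities. There is no concurrent control, so the comparison is only as credible as the likeness of the two populations. If the omitted patients had more complications than average, the difference would favour olesoxime.

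**Working it through.** **1. Who is left out.** The schedule in Protocol Appendix 1 places MFM at baseline, Visit 3 (Week 26), Visit 5 and later visits, and at treatment completion or early discontinuation. SAP 4.4 counts early-discontinuation assessments, and its first window runs from Day 2 to Day 274. The dosed patients outside ITT are therefore those who die before any post-baseline MFM and those who leave without doing one, including at the discontinuation visit.

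**2. Whether the comparator has a matching condition.** It does not. The two-MFM rule in SAP 4.1.3 belongs to the historical comparison population used for the MFM analysis, not to the population in 4.1.5.

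**3. Size.** The plan gives no event count, rate or number excluded for this endpoint, so there is no figure to reproduce. What follows is illustration on assumed inputs, using the SAP formula: rate = events / patient-years × 100.

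*Setting A (assumed):* 120 patients followed for 2 years = 240 patient-years, with 6 events of one lowest level term. Each excluded patient adds one such event and 0.25 years.

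*Setting B (assumed except N):* N = 119, the former TRO19622CLEQ1275-1 patients with a BN29854 baseline sample (Protocol 1.2.2). Five are excluded. The other 114 are followed for 2 years plus 28 days: 114 × (2 + 28/365.25) = 236.7 patient-years. Each excluded patient is followed for 13 weeks plus 28 days: 5 × 119/365.25 = 1.63, giving 238.4 in total. The ITT rate is taken as about 5 (rare) or 50 (common) per 100 patient-years.

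| Case | ITT rate | All dosed patients | ITT / all dosed |
|---|---|---|---|
| A, 2 excluded, 1 event each | 6/240 = 2.50 | 8/240.5 = 3.33 | 0.75 |
| A, 1 excluded, 1 event | 6/240 = 2.50 | 7/240.25 = 2.91 | 0.86 |
| B, rare, 1 event each | 12/236.7 = 5.07 | 17/238.4 = 7.13 | 0.71 |
| B, common, 1 event each | 118/236.7 = 49.8 | 123/238.4 = 51.6 | 0.97 |
| B, rare, no events | 12/236.7 = 5.07 | 12/238.4 = 5.03 | 1.007 |
| None excluded | – | – | 1.00 |

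A wider grid used N = 119 or 171 (171 is the maximum in Protocol 3.1.1), 1 or 2 years of follow-up, 2, 5 or 10 excluded, and 1 or 3 events each. The ratio runs from 0.17 to 0.90 for the rare category and from 0.68 to 0.99 for the common one. The low ends need 10 excluded patients with 3 events each.

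**4. Reading.** The effect is concentrated in sparse categories. That matters because the rates are presented by lowest level term, where counts are likely to be small.

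**The case against.** A reader might infer that every early death and drop-out is removed from the olesoxime side. The documents do not support that. Protocol 4.4.16 asks patients who stop to attend an early discontinuation visit whatever the reason, MFM is scheduled there, and SAP 4.4 counts it. A drop-out who does that MFM stays in ITT. The visit does not help patients who die before any post-baseline MFM, or those who do not attend.

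A reader might also infer that the comparison is biased in favour of olesoxime. Neither size nor direction is established. Protocol 4.5.1 allows withdrawal for any reason, no reasons for early stopping are reported, and excluded patients without events would push the olesoxime rate slightly up. Even the 25% case lies within sampling error: the exact 95% interval for 6 events in 240 patient-years is about 0.9 to 5.4 per 100, which contains 3.3.

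Nor do the events vanish from the report. SAP 4.2.1 gives the number excluded from ITT by reason, and SAP 4.6 summarises adverse events and deaths on the safety population. This makes the problem visible but does not repair the comparison, because those tables are not the ones set against NatHis-SMA.

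Finally, SAP 2.1.2 classes complications as a secondary efficacy measure, ITT is the plan's primary efficacy population, and the analysis is descriptive without hypothesis tests. The choice follows the plan's own rule. That explains it, but does not make an MFM condition suitable for an event rate.

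**Conclusion.** The concern holds as a mismatch of populations: a post-baseline MFM is required on the olesoxime side only, and nothing elsewhere in the documents removes it. Confidence in that is high, because it rests on the definitions alone.

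The consequence is conditional. The documents do not give the number of treated patients without a post-baseline MFM, or their events. If their event rate was above average, the olesoxime rate is biased downward. In the assumed cases with one event per excluded patient, this is about 14% to 29% for a rare term and about 3% for a common category. More exclusions or more events per patient enlarge it. If they had no events the rate is raised by under 1% in the case shown, and with no exclusions there is no bias. The change is worth making because it is cheap and removes a condition that has no function in this analysis.

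**What to change.** - At both mentions of ITT in SAP 4.4.2.4, use the safety population for the incidence tables and the patient-year rates.
- In SAP 4.1.5, derive the NatHis-SMA age limits from that same population, so that the two definitions stay aligned. Otherwise keep the comparator as all enrolled patients in the age and type range.
- Report, for treated patients without a post-baseline MFM, their number, SMA related events and patient-years.
- Keep the ITT version as a supplementary table.

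The cost is small: edits in two SAP sections, a changed population flag and a short extra table, with no new data. The downside for the sponsor is that the olesoxime rate may look less favourable.
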